provide measures of product use (CPD; e-cigarette puff count from device), withdrawal, craving, affect and satisfaction (reinforcement). The other is a random EMA assessment that will occur twice a day and will provide real-time measures of these same constructs (see Appendix II). To limit assessment burden, once daily diary assessments will occur in phases 2, 3, & 4, whereas by design, the user initiated and random EMA assessments occur only in phases 3 & 4. In the U54 preliminary study, an interactive voice response system was used to collect daily CPD. Here, we use the smartphone-implemented diary to collect CPD because we believe that it will provide superior reliability, as well as other advantages described below. The random EMA assessments are limited to phases 3 & 4 because our *primary* interest in these assessments is to longitudinally explore withdrawal, craving, affect and satisfaction related to dual product use among DS and ITS, including the differential effects of ECIG dose. EMA while smoking regular cigarettes has been thoroughly studied in DS and ITS by Shiffman and colleagues [70, 71, 73, 75, 76] and need not be replicated here.

Our smart phone assessments are modeled after several of our previous studies in which we enrolled very diverse smoking populations [88, 90, 94]. We will make modifications to accommodate the ITS as outlined by Shiffman [70, 73] and provide training to participants relevant to each assessment type and study phase (see Appendices PP and RR).

The daily diary assessments will occur 30 minutes after waking and will assess 6 measures from the previous day, including CPD (VLNCC/UB), 8 items based on the QSU, PANAS and MMWS to assess withdrawal, craving, affect (negative and positive) and satisfaction. For the random EMA assessments (phases 3 & 4 only), participants will be prompted to complete up to 2 assessments associated with product use (based on smoking rate-see below). To enhance compliance, the smartphone will provide immediate feedback, as described in the compensation section below.

For the random assessments, each day will be divided into 2 blocks. Within each block, 1 EMA assessment will be randomly triggered to assess withdrawal, craving, affect, and reinforcement. The software prevents random assessments from occurring within 15 minutes of other assessments. Because prompts may occur at inconvenient times, participants can choose to not participate in that random assessment.

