***Aim 2 (Exploratory): To explore the effects of switching to VLNCCs plus ECIG-Hi or ECIG-Lo nicotine doses on abuse liability using biochemical measures of product use, compensation, and toxicant exposure, and self-reported measures of withdrawal, craving, affect, and satisfaction.*** On an exploratory basis, we will examine the differences of ECIG dose (VLNC+ECIG-Lo vs. VLNC+ECIG-Hi) on additional measures of abuse liability, including ECIG puff count, withdrawal, craving, negative affect, minor tobacco alkaloid (MA) levels, acrolein DNA adduct levels, expired CO, RRE (i.e., purchase tasks), and liking (implicit attitudes, perceived harm, product satisfaction ratings). To address this exploratory aim, we will first use GLMM to evaluate the effects of ECIG dose on the retrospective questionnaire (weekly MNWS, PANAS, QSU) and daily diary (i.e., ecological momentary assessment [EMA]) measures of ECIG puff counts, withdrawal craving affect and satisfaction. To analyze the EMA data of these same constructs, we will use generalized time-varying effect modeling (TVEM)

[131, 132], using the TVEM SAS Macro [133], to evaluate the functional form of these measures of abuse liability over time between high and low ECIG conditions and between ITS and DS groups. These models fit a generalized mixed model with a spline function for characterizing changing abuse liability for the within-subjects conditions (using randomized counterbalancing to address order effects) [134, 135]. Moreover, GLMM will evaluate volatility, as defined by defined by Cofta-Woerpel and colleagues [88], as a function of ECIG dose. Conservatively assuming 15% attrition, 75% compliance and a minimum of five daily EMA measures, each 3-week ECIG dose period should provide n= 5355 observations for each group of ITS and DS smokers respectively. As such, TVEM analyses of EMA-sampled data should have sufficient power for these analyses. We will also use GLMM to evaluate the effects of ECIG dose on measures of minor tobacco alkaloid (MA) levels, acrolein DNA adduct levels, expired CO levels, RRE (i.e., purchase tasks), and liking (implicit attitudes, perceived harm, product satisfaction ratings).

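### The Aim 2 TVEM observation count assumes at least five EMA measures a day, but the schedule provides two random prompts, or three assessments with the diary

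*Combined protocol and SAP*

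**What the plan says.** In Statistical Approach & Expected Outcomes, under Aim 2, the plan assumes 15% attrition and then states "75% compliance and a minimum of five daily EMA measures, each 3-week ECIG dose period should provide n= 5355 observations" for ITS and for DS. The next sentence draws a conclusion from that count: "As such, TVEM analyses of EMA-sampled data should have sufficient power for these analyses". No enrolled number is given there.

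The schedule is set out in Measures, under the smartphone assessments. Besides a once-daily diary in phases 2 to 4, it says "The other is a random EMA assessment that will occur twice a day", and later "For the random assessments, each day will be divided into 2 blocks", with one prompt triggered in each block. Financial Compensation for Behavioral Assessments pays for at most two EMA assessments a day in phases 3 and 4. Duration of product exposure, in the Potential Problems section, repeats the maximum of two. Table 4 lists two EMA types only: random assessments and the daily diary.

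Two phrases in Measures are less clear. One says that "the user initiated and random EMA assessments occur only in phases 3 & 4" but gives no number for the user-initiated kind. The other reads "For the random EMA assessments (phases 3 & 4 only), participants will be prompted to complete up to 2 assessments associated with product use".

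**The concern.** A stated minimum of five a day lies above the scheduled maximum of two, or three with the diary. Because the five multiplies straight through the calculation, the count is inflated in proportion, and the sufficiency statement that follows rests on it.

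The text also leaves open which records enter the TVEM. Aim 2 calls the diary a form of EMA, in the words "daily diary (i.e., ecological momentary assessment [EMA]) measures of ECIG puff counts", yet analyses it by GLMM and then assigns the EMA data on the same constructs to TVEM. On that reading the diary would not contribute to the TVEM, and two a day is the closer figure.

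At stake is the stated justification for an exploratory analysis that compares dose conditions and the ITS and DS groups. It matters most for ITS, which is expected to be the smaller group.

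**Working it through.** **Inputs**
- Attrition 15%, compliance 75%, five measures a day: Aim 2 text in Statistical Approach & Expected Outcomes.
- Dose period of 3 weeks = 21 days: Study overview.
- Two random prompts a day, plus one diary: Measures.
- Enrolled n per group: not stated in Aim 2. For ITS, Study overview gives 80 as a ceiling and the Power analysis gives 80 as a floor.

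**Formula**

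Observations per group per period = n enrolled x (1 - attrition) x compliance x assessments per day x days.

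**The plan's figure**

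Solving for n: 5,355 / (0.85 x 0.75 x 5 x 21) = 80. Forward: 80 x 0.85 x 0.75 x 5 x 21 = 5,355 exactly. The 80 is therefore an inference, but it is the only enrolled number that returns the stated figure from the stated inputs.

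**The same formula on the schedule, n = 80**
- Two prompts a day: 80 x 0.85 x 0.75 x 2 x 21 = 2,142, which is 40% of 5,355.
- Three a day with the diary: 80 x 0.85 x 0.75 x 3 x 21 = 3,213, which is 60%.
- At 100% compliance: 80 x 0.85 x 2 x 21 = 2,856, or 80 x 0.85 x 3 x 21 = 4,284. Both are still below 5,355.

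**Per retained participant per period**
- Two a day: 0.75 x 42 = 31.5.
- Three a day: 0.75 x 63 = 47.25.
- Implied by the plan: 0.75 x 105 = 78.75.

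**Enrolment needed to reach 5,355 at 15% attrition**
- Two a day: 5,355 / (0.85 x 0.75 x 42) = 200 per group.
- Three a day: 5,355 / (0.85 x 0.75 x 63) = 133.3, so 134 per group.

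**Daily smokers, if more than 80**

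Assume all 380 are enrolled, with 80 ITS and 80 in the JUUL arm: 380 - 80 - 80 = 220 eGo daily smokers. Then 220 x 0.85 x 0.75 x 42 = 5,890.5, about 5,891, which exceeds the stated figure.

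**Illustration at the interim retention of 77%** (reported under Safety of VLNC cigarette and ECIG products, not split by group)
- n = 80: 80 x 0.77 x 0.75 x 42 = 1,940; with the diary, 80 x 0.77 x 0.75 x 63 = 2,911.
- n = 220 DS: 220 x 0.77 x 0.75 x 42 = 5,336.

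**Cross-check from the payments**

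Participant Compensation caps EMA payments at USD 378. At USD 2 per diary over 63 days (phases 2 to 4) and USD 3 per EMA assessment, two a day over 42 days (phases 3 and 4): 63 x 2 + 84 x 3 = 126 + 252 = 378. The budget matches one diary plus two prompts a day exactly.

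**The case against.** The strongest reply is that the total number of entries per day is undefined rather than shown to be two or three. Measures names user-initiated entries and refers to assessments tied to product use. The payment check covers only paid assessments, so unpaid entries would leave the USD 378 unchanged. This is fair as far as it goes: the counts of 2,142 and 3,213 leave out any user-initiated entries. It does not rescue the sentence, because an entry type with no number, no payment and no row in Table 4 cannot support a guaranteed minimum. If the product-use assessments were read as separate from the random prompts, one diary plus two plus two would make five a maximum. At the same USD 3 rate, which is an assumption, the budget would then be 63 x 2 + 168 x 3 = USD 630.

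A second reply is that the shortfall is not shown for both groups. That stands. It applies to ITS if about 80 are enrolled, and the DS total may be met. If 80 is a floor for ITS, the size of the ITS shortfall is not fixed either.

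Third, the 77% figure is retention to the end of the study, whereas the count is per dose period. Someone who leaves during phase 4 still contributes phase 3 data, so the counts at 77% may be too low. They are illustrative only, and the finding does not depend on them.

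Finally, the consequence is limited. The plan gives no effect size or within-person correlation for the TVEM, so the drop in observations cannot be turned into a loss of power. The Power analysis separately notes that the TVEM will have far more observations than the GLMMs for self-report and volatility measures. That also stands. For the same reason, the count alone cannot establish that power is sufficient.

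**Conclusion.** The concern holds, as a minor one. The daily number behind 5,355 conflicts with the plan's own schedule. If 80 are enrolled in a group, and on the plan's 15% attrition and 75% compliance, the scheduled assessments yield 2,142 observations per period from the random prompts, or 3,213 with the diary. The conflict in the daily number is certain. The replacement counts depend on the inferred 80 and on there being no further entry type. The sufficiency sentence therefore lacks the support it cites, but inadequate TVEM power has not been shown. Aim 2 is exploratory, and neither the Aim 1 sample size nor the GLMM power statement (f = 0.17 with 67 daily smokers) uses this count.

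**What to change.** Reconcile the Aim 2 text with the smartphone schedule in Measures, the compensation paragraph and Duration of product exposure:

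- State which entry types enter the TVEM: random prompts, the daily diary, and any user-initiated or use-linked entry. Define the number per day for any type beyond the first two.
- Replace the minimum of five with the scheduled number: two, or three if the diary is counted, unless a further type is defined.
- State the enrolled n assumed for ITS and for eGo DS separately, after settling whether 80 ITS is a ceiling (Study overview) or a floor (Power analysis).
- Recompute the count for each group, and show it at 77% retention as a sensitivity figure, labelled as end-of-study retention.
- Delete the sentence claiming sufficient power, or restate it as an expected number of observations.

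The cost is wording and a recount. The schedule, participant burden, analysis method and Aim 1 are unchanged. The stated count for ITS will be less favourable if 80 are enrolled; the DS count may not fall.

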nicotine, the primary psychoactive constituent of tobacco smoke. Nicotine directly activates brain reward circuits [13] that enhance self-administration [14] and stimulates multiple neurotransmitter systems throughout the brain that play a critical role in modulating affect, attention, and cognitive performance [15–18]. Repeated nicotine use leads to dependence, during which smoking may be triggered by the presence of aversive withdrawal symptoms that emerge when brain nicotine levels decrease [19, 20] and/or the presence of motivationally relevant cues associated with craving, stress, and particularly negative affect [21–23]. Avoidance of these conditions prompts further nicotine use, which results in the compulsive pattern of nicotine-seeking behavior that characterizes the addictive process [18, 24, 25]. Smoking behavior is thought to reflect an attempt at maintaining an "optimum" level of nicotine in the brain that maximizes its subjective effects (both liking and wanting) and minimizes withdrawal symptoms [26]. This is supported by studies that have varied the nicotine yield of cigarettes. The typical nicotine yield of commercially available cigarettes is approximately 0.8 mg/cigarette [27]. When this is reduced to levels as low as 0.3 mg, some smokers compensate for the reduced nicotine yield by smoking more cigarettes or by extracting more nicotine per cigarette by increasing puff volume and duration [11, 28–31].

For those who smoke daily, it is thought that a minimum level of nicotine is required to maintain dependence. Below this minimum, brain reward circuitry may not be sufficiently activated and over time, nicotine-self administration may undergo extinction [32]. Thus, a promising regulatory/treatment approach for reducing the abuse liability of cigarettes may be lowering nicotine content to a level below what is required to maintain dependence [26]. In the past, commercially available VLNCCs typically had nicotine levels below 0.1 mg. When transitioned to these VLNCCs, smokers may initially compensate for the nicotine loss via increased smoking [33], but over time the total VLNCCs consumed is expected to decrease because nicotine levels may be insufficient to reinforce continued high levels of smoking [11, 30, 31, 34].

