##### **Study overview**

Participants will be up to 380 (including up to 80 intermittent [ITS]) non-treatment-seeking adult smokers who are not regular e-cig users. Participants will smoke their usual brand (UB) during Phase 1 (Baseline; week 1) and will exclusively smoke the VLNCC during Phase 2 (weeks 2-4). During phases 3 (weeks 5-7) & 4 (weeks 8-10), smokers will be instructed to freely use any combination of assigned VLNCC and e-cigs (VLNCC+ECIG). All subjects will receive both e-cig doses (ECIG-Hi [36 mg/ml] and ECIG-Lo [8 mg/ml]) with order counter balanced across phases 3 and 4. At least 80 daily smokers will be randomized to the JUUL condition (VLNCC for phase 2 and combined VLNCC+JUUL-Hi or -Lo for phases 3 & 4). All participants in the JUUL group will receive both e-cig doses (JUUL-Hi [JUUL 5%; 59 mg/ml nicotine] and JUUL-Lo [JUUL 3%; 35 mg/ml nicotine]), with order counter-balanced across phases 3 and 4.

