**Assessment of nicotine abuse liability.** We will be measuring abuse liability using multiple domains. In terms of the 5 abuse liability domains described by Carter and colleagues , we will be capturing 4, including acute dose-effect comparisons (ECIG-Hi vs. ECIG-Lo), suppression of withdrawal and craving (in-session withdrawal and affect questionnaires; EMA measures of withdrawal, craving, affect), self-administration (RRE; nicotine compensation: TNE, MA, expired CO), and choice procedures (product choice between VLNCC and ECIG during dual use phases). For Aims 1 and 2, we will assess abuse liability in terms of nicotine compensation (i.e., urinary TNE and MA, expired CO) and product use, product liking (i.e., implicit attitudes, perceived harm, satisfaction), and RRE (i.e., purchase task valuation) at the end of each study phase. To assess product use for Aims 1 and 2, participants will be provided with smartphones prior to the start of phase 2 for once daily recording of CPD (also a primary outcome) and e-cigarette use (puff counts from device). For Aim 3, we take a multi-modal approach to the measurement of withdrawal, craving, affect and satisfaction (reinforcement) which provides progressively more sensitive assessments that range from traditional measures (questionnaires filled out weekly) to the smartphone daily diary (patients overall assessment of the day) to real-time measures captured through EMA. Questionnaires will be administered at each of the 5 in-person sessions, smartphone daily diary will be collected during phases 2, 3, and 4, and smartphone EMA assessments will be conducted in phases 3 and 4 only.

**COVID-19 adaptation:** Enrolled participants will be mailed free study smartphones prior to the start of phase 2 to be used for the duration of their participation in the study.

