**Aim 3 (exploratory): To explore the effects of switching from usual-brand cigarettes to VLNCCs, and from VLNCCs to VLNCC+ECIGs on measures of abuse liability.** On an exploratory basis, we will examine potential changes in the abuse liability measures from Aims 1 & 2 between the UB cigarette and VLNCC only phases, and between those phases and the dual-use phases (VLNC+ECIG-Lo and VLNC+ECIG-Hi). We will use GLMM to evaluate the study phase (UB cigarettes, VLNCCs, VLNC+ECIG-Lo, VLNC+ECIG-Hi) and the measures of abuse liability from Aims 1 & 2 to characterize the impact of transitioning between study nicotine products over time.

**Aim 4 (exploratory): To characterize the effects of dual use of VLNCC and JUUL ECIGs on abuse liability.** On an exploratory basis, we will examine the differences in measures of abuse liability between the two phases of dual-use (VLNC+JUUL-Lo vs. VLNC+JUUL-Hi) among participants assigned to the JUUL ECIG arm. We will use GLMM to evaluate the effects of JUUL dose on measures of nicotine abuse liability, including patterns of product use (UB and VLNCC CPD, ECIG puff count), nicotine compensation (TNE, MA, expired CO), product liking (IAT, Product Evaluation Scales, perceived harm, PHR), RRE (Purchase Task indices).

**Power analysis.** Sample size determination for the current proposal focuses on our primary outcomes for the Aim 1 hypothesis. Effect size estimates are based on our U54 data using the usual brand baseline and 0.03 mg VLNCC conditions to estimate CPD and TNE from those two conditions, respectively [9]. There is no extant data to draw upon for VLNCC+ECIG-Hi or ECIG-Lo conditions for either DS or ITS. Hence, we attempted to estimate the means and standard deviations for CPD and TNE for these two conditions using data from the U54, using

**Table 1.** Anticipated effects for DS and ITS, by Phase and E-Cig group.

Primary Outcome	Phase 1: Usual Brand	Phase 2: VLNC Only	Phase 3: VLNC + ECIGs-HI	Phase 4: VLNC + ECIGs-LO
DS				
CPD	19.62 (10.18)	14.19 (10.09) a	12.80 (10.00) b	12.80 (10.00) b
TNE	63.01 (55.87)	33.54 (34.84)	59.50 (53.88)	33.08 (31.27)
log(TNE)	3.89 (0.99)	2.69 (1.65) a	3.60 (1.28) c	2.72 (1.62) b
ITS				
CPD	3.42 (3.44)	2.47 (3.44) a	1.57 (3.44) c	1.57 (3.44) c
TNE	32.5 (17.53)	10 (9.36)	28.37 (22.24)	15.88 (11.16)

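### Aim 3 words non-randomised phase differences as effects of switching product, although product and elapsed time coincide in a sequence that every participant follows

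*Combined protocol and SAP*

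**What the plan says.** **Aim.** In Statistical Approach & Expected Outcomes, Aim 3 is "To explore the effects of switching from usual-brand cigarettes to VLNCCs, and from VLNCCs to VLNCC+ECIGs on measures of abuse liability". The same wording stands in the Specific Aims. It is labelled exploratory and carries no hypothesis.

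**Model.** "We will use GLMM to evaluate the study phase (UB cigarettes, VLNCCs, VLNC+ECIG-Lo, VLNC+ECIG-Hi"), the purpose being "to characterize the impact of transitioning between study nicotine products over time". No period or time term is named.

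**Sequence.** Study overview: "Participants will smoke their usual brand (UB) during Phase 1 (Baseline; week 1) and will exclusively smoke the VLNCC during Phase 2 (weeks 2-4"), followed by VLNCC plus e-cigarette in weeks 5-7 and 8-10. "All subjects will receive both e-cig doses", and only their order is counterbalanced. The JUUL arm follows the same sequence with its own two doses. No arm remains on usual brand (UB) or on VLNCC alone.

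**Expected trend.** The Review of Relevant Literature says that smokers may compensate at first, but "over time the total VLNCCs consumed is expected to decrease because nicotine levels may be insufficient" to sustain heavy smoking.

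**Stability.** Under Duration of product exposure (Potential Problems & Alternative Strategies), earlier work is said to show that cigarettes per day (CPD) on VLNCC moved little after the third week. This is offered in support of the three-week phases, not of Aim 3.

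**Data.** "smartphone daily diary will be collected during phases 2, 3, and 4". Home urine for total nicotine equivalents (TNE) and minor alkaloids is planned twice a week between visits. The COVID-19 adaptation cuts this to one sample near each visit.

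**The concern.** An effect of switching is a statement about what would have happened without the switch. For VLNCC v dual use, that means the same weeks spent on VLNCC alone. Nobody in this trial supplies that information, so a decline that would have continued on VLNCC alone looks the same as e-cigarettes displacing cigarettes.

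This matters because the protocol intends to use these contrasts. Future directions says that the project will have established how far smokers make up lost nicotine with e-cigarettes. The biomarker section makes TNE the main measure of compensation between baseline and the later conditions. In Table 2, three of the four contrasts in each smoker group are non-randomised phase contrasts. The Potential Problems section discusses phase length, flavour and safety, but not the fixed order.

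**Working it through.** **1. The plan's own figure.** Table 2 gives 85.7% power for log(TNE), VLNCC v VLNCC+ECIG-Lo, intermittent smokers (ITS). Inputs are the Table 1 means 1.74 and 2.31, SDs 1.49 and 1.29, correlation 0.4 and n = 67.

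d_z = (2.31 − 1.74) / √(1.49² + 1.29² − 2 × 0.4 × 1.49 × 1.29) = 0.57 / √2.3465 = 0.372 (stated 0.37).

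Two-sided 5% paired t test: 85.1%; normal approximation: 86.1%. The figure reproduces. The power is not in question; what matters is what the contrast measures.

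**2. What the design can estimate.** There are two sequences: (UB, VLNCC, Hi, Lo) and (UB, VLNCC, Lo, Hi).

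- Phase-only model: 4 columns, rank 4. Every contrast is estimable, but only because time effects are set to zero.
- Add a period factor: 7 columns, rank 5. The VLNCC column equals the period 2 column, and Hi + Lo equals period 3 + period 4, so two columns are lost. UB v VLNCC, VLNCC v Hi and VLNCC v Lo are no longer estimable. Hi v Lo still is.
- A strictly linear time term gives rank 5 of 5, but its slope comes from Phase 3 v Phase 4 and is projected back to weeks 1-4.

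**3. Elapsed time in the contrast.** Visits 1 to 4 fall on days 8, 29, 50 and 71 (Table 4). The midpoints of Phases 2, 3 and 4 are days 18.5, 39.5 and 60.5. The mean gap from Phase 2 to dual use is (21 + 42)/2 = 31.5 days = 4.5 weeks.

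**4. CPD drift that would equal the Table 1 change** (back-solved; no rate is documented).

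- Daily smokers (DS): (14.19 − 12.80)/4.5 = 1.39/4.5 = 0.31 CPD a week.
- ITS: (2.47 − 1.57)/4.5 = 0.90/4.5 = 0.20 CPD a week.

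**5. log(TNE).** Table 1 expects rises on adding e-cigarettes: DS Hi 2.69 to 3.60, ITS Hi 1.74 to 3.07, ITS Lo 1.74 to 2.31. A background fall would mask these. For scale, the DS VLNCC v Hi difference has SD √(1.65² + 1.28² − 0.8 × 1.65 × 1.28) = 1.634. The minimum detectable d_z of 0.35 is then 0.572 log units, or 0.572/4.5 = 0.127 a week. With no product effect and assumed drifts of 0, 0.05, 0.10 and 0.15 log units a week, the two-sided contrast rejected in 6%, 21%, 60% and 92% of simulated trials (n = 67).

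**6. Settling within Phase 2, and which adjustment copes with it.** Assume no e-cigarette effect and DS CPD on day t of VLNCC use equal to 14.19 + (19.62 − 14.19) × 0.5^(t/h). CPD then levels off as the Duration section suggests. Apparent e-cigarette effect in CPD (the true value is 0):

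| Method | h = 3 days | h = 7 days |
|---|---|---|
| Dual use minus whole Phase 2 | −1.2 | −2.2 |
| Dual use minus last week of Phase 2 | −0.1 | −0.9 |
| Linear Phase 2 trend carried forward, mean over Phases 3-4 | +5.5 | +4.8 |
| Level and slope change, step at Visit 2 | +1.1 | +0.5 |

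The fitted Phase 2 slope is about −1.5 to −1.6 CPD a week. Projecting it through six more weeks causes the large false rise.

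**The case against.** The best reply is that Aim 3 is exploratory, states no hypothesis and already speaks of changes between phases over time, and that CPD is reported to be stable after the third week on VLNCC. If so, the end of Phase 2 is a nearly clean comparator. The drift rates in step 4 are back-solved and need a steady decline to week 10. The DS CPD change is also one that Table 1 does not expect to be significant.

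Much of this stands. The stability report does lessen the concern for CPD after Phase 2. But it comes from earlier data, covers CPD only, and begins about where Phase 2 ends. It says nothing about change inside the comparator phase, and step 6 shows that settling there can matter even when CPD is flat afterwards. The exploratory label does not license causal wording.

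Four stronger readings are tempting, and the documents do not support them:

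- A reader might infer that a fall in CPD on dual use would be an artefact. No drift is documented; the point is that the planned model could not tell.
- A reader might infer that drift always flatters e-cigarettes. For log(TNE), a fall works against the expected rises.
- A reader might infer that the primary result is compromised. Hi v Lo is counterbalanced and stays estimable with period effects.
- A reader might infer that a linear Phase 2 trend plus one step would recover the e-cigarette effect. Under a levelling-off curve it misleads more than the raw contrast.

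**Conclusion.** The point holds for every non-randomised Aim 3 contrast: the phase-only GLMM cannot separate product from elapsed time. That follows from the design alone and needs no assumption about drift.

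The size of any bias is unknown. The illustrative 0.31 (DS) and 0.20 (ITS) CPD a week assume a steady linear fall. The settling curves in step 6 assume a half-life of 3 to 7 days and a plateau at 14.19 CPD. They put the whole-phase error at 1.2 to 2.2 CPD, against an anticipated DS change of 1.39. The statistical section does not say which diary days make up the Phase 2 value, so this error may or may not arise.

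The consequence is limited to an exploratory aim and the conclusions drawn from it. Aim 1 is unaffected.

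**What to change.** 1. **Wording.** Describe Aim 3, and conclusions resting on it such as those in Future directions, as within-person change across a fixed sequence for all non-randomised contrasts. State that product and time coincide.
2. **Sensitivity analysis for VLNCC v dual use.** Use the Phase 2-4 diaries, and the twice-weekly home urine for TNE and minor alkaloids where it was collected. Show within-phase trends. Compare the last week of Phase 2 with the dual-use phases. Fit a segmented GLMM with changes in both level and slope at Visit 2, and a non-linear Phase 2 trend as a check. Step 6 shows that the linear segmented model alone can still be off by 0.5 to 1.1 CPD.
3. **What not to report.** Do not present a linear Phase 2 trend carried forward with a single step as the e-cigarette effect.

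UB v VLNCC has no such rescue: the diary starts only in Phase 2, and nobody stays on usual brand. For that contrast the rewording is the remedy.

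No new arm, visit or sample is needed. The cost is a little more analysis, less precise estimates and a weaker claim for Aim 3.
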